2.4.2.4 Additional systemic cGvHD therapy

New additional systemic cGvHD therapy (medications and procedures) since start of study treatment will be listed and summarized by lowest ATC class, preferred term, overall and by Age group by means of frequency counts and percentages using FAS.

Initiation of systemic CNI at the time of or after start of study treatment despite absence of lack of efficacy will be counted as new additional systemic treatment. Note: Although the protocol does not explicitly prohibit initiation of systemic CNI at time of randomization or initiation of study treatment potential impact of CNI on efficacy outcome in responders cannot be excluded.

See Appendix [Section 5.4.3](#) for more detailed specifications.

2.4.2.5 Concomitant medications

Concomitant therapy is defined as all interventions (therapeutic treatments and procedures) other than the study treatment administered to a patient coinciding with the study treatment period. Concomitant therapy includes medications (other than study drugs) starting on or after the start date of study treatment or medications starting prior to the start date of study treatment and continuing after the start date of study treatment.

Concomitant medications will be coded using the World Health Organization (WHO) Drug Reference Listing (DRL) dictionary that employs the WHO Anatomical Therapeutic Chemical (ATC) classification system and summarized by lowest ATC class and preferred term using frequency counts and percentages. Surgical and medical procedures will be coded using MedDRA and summarized by SOC and preferred term. The summaries using Safety Set will include:

- Medications starting on or after the start of study treatment but no later than end of on-treatment period; and
- Medications starting prior to start of study treatment and continuing after the start of study treatment.

All concomitant therapies will be listed using Safety Set. Any concomitant therapies starting and ending prior to the start of study treatment or starting beyond end of on-treatment period will be flagged in the listing.

In addition, a subset of concomitant medications i.e. hemopoietic cytokines and transfusions (red blood cells and platelets) will be grouped and summarized by Age group.

2.4.2.5.1 Calcineurin inhibitors (CNIs) during study treatment

The duration of exposure will be summarized for systemic CNIs (cyclosporine or tacrolimus) up to end of on-treatment period by Age group. It will also be categorized into time intervals; frequency counts and percentages will be presented for the number (%) of patients in each interval. These analyses will be based on Safety Set.

2.5 Analysis of the primary objective

Analyses of the primary endpoint and related supportive analyses will not be repeated for the final CSR, if data has not changed compared to interim database lock.

The primary objective of the study is to evaluate the activity of ruxolitinib added to standard dose corticosteroids +/- CNI in pediatric subjects with moderate or severe treatment naïve-cGvHD or SR-cGvHD measured by **Overall Response Rate (ORR)** at Cycle 7 Day 1 based on all subjects in the study. The analysis will be performed based on FAS.

2.5.1 Primary endpoint

The primary efficacy variable of the study is **overall response rate (ORR)** at Cycle 7 Day 1, defined as the proportion of subjects demonstrating a complete response (CR) or partial response (PR), according to the NIH Consensus Criteria ([Lee et al 2015](#)) as reported in the CRF. Note that response is relative to the assessment of cGvHD at baseline.

- **Complete response** is defined as complete resolution of all signs and symptoms of cGvHD in all evaluable organs without initiation of any new systemic therapy.
- **Partial response** is defined as an improvement in at least one organ (e.g. improvement of 1 or more points on a 4 to 7 point scale, or an improvement of 2 or more points on a 10 to 12 point scale) without progression in other organs or sites, or initiation/ addition of new systemic therapies.
- **Lack of response** is defined as unchanged, mixed response, or progression. (Please refer to Table 8-3 and Table 16-3 in the protocol for the definitions of "unchanged", "mixed response" and "progression".)

cGvHD Flare and **cGvHD Recurrence** are not considered as a treatment failure, unless they require a change or addition of another systemic treatment defined as below.

- **cGvHD Flare** is defined as any increase in symptoms or therapy for cGvHD after an initial response (CR or PR). A cGvHD flare is not considered a treatment failure unless a change or addition of another systemic treatment, including CNIs, occurs.
- **cGvHD Recurrence** is defined as the return of cGvHD disease after tapering off study treatment due to response. Following completion of a taper of systemic therapy, if worsening of cGvHD symptoms occur, the patient is allowed to resume treatment for cGvHD as per local institutional practice. For the statistical analyses, re-start of treatment for cGvHD is handled in the same way as addition or initiation of new systemic treatment.

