8.3.1.2.1 Baseline Organ involvement

The chronic GvHD assessment is a global and organ-specific clinician assessment which focuses on symptom activity in chronic GvHD subjects. The assessment collects individual organ symptoms (eyes, mouth, lungs, gastrointestinal, liver, skin, joints and fascia). Details and specifics of some organ assessments at C1D1 (baseline) differ to those for staging (for e.g. skin, gastrointestinal) and therefore cGvHD staging and baseline organ assessments must be completed independently. Assessments for all organs must be performed prior to treatment assignment at the Cycle 1 Day 1 visit (baseline). The list of organ-specific assessments and scoring can be found in [Section 16.3](#).

Skin

Skin features are first to be assessed by % body surface area (BSA), presence of skin abnormalities (maculopapular rash/erythema, papulosquamous lesion or ichthyosis, lichen planus - like features, sclerotic features, keratosis pilaris – like,), skin feature score, and skin and/or joint tightening severity. These assessments will populate the overall skin organ score in the eCRF.

Eyes

The eye score is determined by assessing severity of dry eye symptoms and degree of vision impairment.

Mouth

Mouth features are first to be scored by %BSA individually for any erythema, lichenoid, and ulcers. The total score for all mucosal changes will populate the overall mouth organ score in the eCRF.

Liver

The baseline liver involvement is assessed using ALT, alkaline phosphates, and total bilirubin. All three liver parameters must be obtained in order for the liver to be assessed. Liver parameters must be obtained comprehensively together with observed values, units and normal ranges documented. Note, staging criteria for liver differs to that of cGvHD liver organ assessments from baseline.

Gastrointestinal tract

Individual GI scores are to be collected for frequency of esophageal symptoms (dysphagia or odynophagia), upper GI symptoms (early satiety, anorexia, or nausea and vomiting), and lower GI (diarrhea). Individual GI scores refers to the week prior to the GI cGvHD assessment being performed.

Lungs

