8.3.1.2.2 Post-baseline organ involvement and cGVHD response assessment

The chronic GvHD assessment will be performed by the treating physician according to the detailed schedule found in [Table 8-1](#). At each post-baseline assessment, each organ must be assessed using the same criteria as for baseline. Additionally, the response evaluation of each organ should be made by comparing the current organ assessment versus the baseline organ status documented on Cycle 1 Day 1. A high level summary of organ-specific response assessment criteria as per NIH consensus guideline ([Lee et al 2015](#)) are listed in [Table 8-2](#).

[Table 8-3](#) summarizes the rules for overall response assessment based on organ-specific evaluations at each scheduled post-baseline visit. These overall response assessments will be used to derive response rates for the primary and secondary endpoints.

More detailed instructions on organ-specific response assessment and overall response evaluation, including examples, are given in [Section 16.4](#).

Table 8-2 Organs included for the post-baseline cGvHD response assessment

Organ	Evaluation by	Criteria for response assessment
Skin	NIH Skin Score, considering %BSA involvement and sclerotic features	Change of skin score
Eyes	NIH Eye Score	Change of Eye score
Mouth	NIH Modified OMRS (Sum of scores for erythema, lichenoid and ulcers)	Change of Oral Mucosa Rating Scale (OMRS)
Esophagus	NIH Esophagus Score	Change of Esophagus score
Upper GI	NIH Upper GI Score	Change of Upper GI score
Lower GI	NIH Lower GI Score	Change of Lower GI score
Liver	Lab results for ALT, alkaline phosphatase, and Total bilirubin	Change of values for ALT, alkaline phosphatase, and Total bilirubin
Lungs	NIH Lung score AND %FEV1	Change of %FEV1 (preferable) or change in NIH lung symptom score
Joints and fascia	NIH Joint and Fascia Score and P-ROM scores	Change of Joint and Fascia Score and P-ROM scores

Table 8-3 Post-baseline overall response evaluation based on all organs

	Organ-specific response ¹				

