16.4.2.1 Liver

Liver response assessment is based on the following chemistry lab parameters: Alanine aminotransferase (ALT), alkaline phosphatase (ALP) and total bilirubin (BILI). All three liver parameters must be obtained in order for the liver to be assessed.

Observed lab values and corresponding ULN at baseline should be documented. Observed post-baseline values will be compared to observed baseline values in order to determine the liver response for the post-baseline visit. The steps to apply the rules per NIH criteria and some examples are displayed in [Figure 16-1](#), [Figure 16-2](#) and [Figure 16-3](#).

Example 1 ([Figure 16-2](#)):

- At baseline ALT and AP are increased ($>$ ULN) and BILI is within the normal range.
- At the post-baseline visit ALT and BILI are within the normal ranges and the value of AP decreased from baseline by 56%: Therefore, the liver response for this visit is assessed as ‘partial response (PR)’.

Example 2 ([Figure 16-3](#)):

- At baseline Alkaline Phosphatase (AP) is increased ($>$ ULN), whereas ALT and BILI are within the normal range.
- At the post-baseline visit all 3 parameters are increased ($>$ ULN) but the absolute increase for each of the parameters is less than the corresponding value of $2 \times$ ULN. Therefore, the Week 4 liver response is considered as ‘unchanged’ from baseline.

Table 16-3 Response determination for chronic GvHD by organ at post-baseline assessment (comparison vs. baseline)

Organ	Complete response ¹	Partial response ¹	Progression ¹	No involvement/unchanged	
				Baseline	Post-baseline
Skin	NIH Skin Score 0 after previous involvement	Decrease in NIH Skin Score by 1 or more points	Increase in NIH Skin Score by 1 or more points, except 0 to 1	Score = 0	Score = 0 or 1
				Equal Scores at both time points	
Eyes	NIH Eye Score 0 after previous involvement	Decrease in NIH Eye Score by 1 or more points	Increase in NIH Eye Score by 1 or more points, except 0 to 1	Score = 0	Score = 0 or 1
				Equal Scores at both time points	
Mouth	NIH Modified OMRS 0 after previous involvement	Decrease in NIH Modified OMRS of 2 or more points	Increase in NIH Modified OMRS of 2 or more points	Equal OMRS at both time points (including Score=0) or change of OMRS from baseline less than 2 points	
Esophagus	NIH Esophagus Score 0 after previous involvement	Decrease in NIH Esophagus Score by 1 or more points	Increase in NIH Esophagus Score by 1 or more points, except 0 to 1	Score = 0	Score = 0 or 1

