				Equal Scores at both time points	
Upper GI	NIH Upper GI Score 0 after previous involvement	Decrease in NIH Upper GI Score by 1 or more points	Increase in NIH Upper GI Score by 1 or more points, except 0 to 1	Score = 0	Score = 0 or 1
				Equal Scores at both time points	
Lower GI				Score = 0	Score = 0 or 1

Organ	Complete response ¹ NIH Lower GI Score 0 after previous involvement	Partial response ¹ Decrease in NIH Lower GI Score by 1 or more points	Progression ¹ Increase in NIH Lower GI Score by 1 or more points, except from 0 to 1	No involvement/unchanged	
				Baseline	Post-baseline
				Equal Scores at both time points	
Liver	Normal ALT, alkaline phosphatase, and Total bilirubin after previous elevation of 1 or more	Decrease by 50%	Increase by 2 x ULN	See text	
Lungs ²	Normal %FEV1 after previous involvement If PFTs not available, NIH Lung Symptom Score 0 after previous involvement	Increase by 10% predicted absolute value of %FEV1 If PFTs not available, decrease in NIH Lung Symptom Score by 1 or more points	Decrease by 10% predicted absolute value of %FEV1 If PFTs not available, increase in NIH Lung Symptom Score by 1 or more points, except 0 to 1	Change of %FEV1 from baseline < 10% (see text for additional rules) If PFTs not available, Score = 0 Score = 0 or 1	
Joint and fascia	Both NIH Joint and Fascia Score 0 and P-ROM score 25 after previous involvement by at least 1 measure	Decrease in NIH Joint and Fascia Score by 1 or more points or increase in P-ROM score by 1 point for any site	Increase in NIH Joint and Fascia Score by 1 or more points or decrease in P-ROM score by 1 point for any site	J&F Score=0 and P-ROM Score=25	J&F Score=0 and P-ROM Score=25 Any situation that does not qualify for response or progression (see text)

¹ response definition as per Table 4 in the published NIH criteria, see [Lee et al 2015](#), ULN indicates upper limit of normal.

² Lung response assessment is determined based on an improvement (e.g. 50% to 60%) or worsening (e.g. 50% to 40%) in %FEV1 of 10% or more predicted absolute value.

Figure 16-1 Criteria to determine liver response: general rules

at baseline visit				at each post-baseline visit		
Observed data	Liver involvement: Any parameter > ULN?	ULN	Calculate UL2= 2 x ULN	- Document observed values for ALT, AP and BIL and compare to baseline values to determine the liver response		
				Observed data	Action	Liver response
				ALT_value AP_value BIL_value		

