16.4.2.3 Joints and fascia

NIH Joint and Fascia score as well as photographic range of motion (P-ROM) score are evaluated.

Involvement at baseline is defined as NIH Joint and Fascia score ≥ 1

A decrease (i.e. worsening) of any site in P-ROM is considered as progression (irrespective of the change in the NIH Joints and Fascia score). Similarly, an increase (worsening) in the NIH Joints and Fascia score is considered as progression (irrespective of the change in any of the 4 P-ROMs)

Accordingly, a partial response is only possible if:

- at least one site in P-ROM increased by 1 or more points
- and all other sites remain unchanged compared to baseline
- and NIH Joints and Fascia score is equal to or decreased from baseline

OR

- Decrease of the NIH Joints and Fascia Score from baseline with NO worsening in P-ROM for any site

Example for progression

[figure not shown]
	Baseline	Post-baseline	
NIH Joints and Fascia Score	1	1	equal
P-ROM			
Shoulder	6	6	equal
Elbow	6	5	decrease
Wrist/finger	6	6	equal
Ankle	3	4	increase
TOTAL	21	21	

Example for partial response

	Baseline	Post-baseline	
NIH Score	1	1	equal
P-ROM			
Shoulder	6	6	equal
Elbow	6	6	equal
Wrist/finger	6	6	equal
Ankle	3	4	increase
TOTAL	21	22	

Photographic Range of Motion (P-ROM)

Figure 16-4 Photographic Range of Motion (P-ROm)

Source: [Lee et al 2015](#)

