2.5.4 Supportive analyses

Supportive analysis will include:

- A detailed description of response rates (CR, PR, Unchanged, mixed response and progression) at Cycle 7 Day 1
- A detailed description of the organ-specific response for all organs at Cycle 7 Day 1
- If at least 18 subjects are enrolled with either first line vs. SR-cGvHD respectively, the ORR will be explored for treatment naive and SR subgroup subjects.
This and further subgroups are described in [Section 2.2.1](#).

The supportive analyses will be performed on the FAS.

In addition, a sensitivity analysis will be done, where subjects with protocol deviations that may affect the primary endpoint are excluded from the analysis. These are following:

- Prohibited concomitant medication administered during treatment period (COMD01)
- Treatment naive or steroid refractory cGvHD corticosteroid treatment criteria not met (INCL04B)
- Missing individual organ assessment at C1D1 (unless not possible) (OTH02)
- Missing individual organ assessment at C4D1 or C7D1 (unless not possible) (OTH03)
- Starting dose of study drug (ruxolitinib) not per protocol-defined age-based schedule (Group 1 and 2) (TRT01)
- Starting dose of study drug (ruxolitinib) not per protocol-defined age-based schedule (Group 3 and 4) (TRT02)
- In treatment naive cGvHD subjects, in addition to ruxolitinib, methylprednisolone (or equivalent prednisone) treatment was initially not given as part of study treatment (TRT03)
- Patient did not take the ruxolitinib assigned dose (TRT08)
- The ruxolitinib dose assigned on C1D1 (based on age) was changed before the subject completed C7D1 assessments (excluding dose adjustments for safety) (TRT09)

- Corticosteroid taper was initiated earlier than allowed as per protocol (excluding dose adjustments for safety) (TRT13)
- Subject had a dose interruption of >21 days from ruxolitinib but was not permanently discontinued from ruxolitinib (WITH01)
- Individual organ response assessment / overall response assessment not as per protocol response criteria (OTH14)
- Patient was not compliant with study drug (Ruxolitinib); More than 7 days of consecutive insufficient treatment or overdosing or cumulated insufficient treatment over a period of 24 weeks is observed (TRT16)

Supportive analysis will be purely exploratory and are intended to explore the consistency of treatment effect. No inferential statistics (p-values) will be produced for the subgroups.

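### The primary response rate rests on the category the unblinded physician enters; no planned analysis derives it from the criteria, and Appendix 4 places some mouth and joint scores in two categories

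*SAP*

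**What the plan says.** SAP 2.5.1 defines the primary variable as the proportion with complete or partial response "as reported in the CRF. Note that response is relative to the assessment of cGvHD at baseline". Protocol 8.3.1.2.2 names the assessor: "The chronic GvHD assessment will be performed by the treating physician according to the detailed schedule found in" Table 8-1. It adds that these overall assessments feed the primary and secondary response rates. Protocol 6.4 leaves everyone who performs assessments unblinded. Under SAP 2.5.3 the entered category is overridden only for a missing or out-of-window assessment or for new systemic therapy.

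SAP 2.5.4 lists, among the deviations that may affect the primary endpoint, "Individual organ response assessment / overall response assessment not as per protocol response criteria (OTH14"). SAP Table 2-3 removes subjects from the Full Analysis Set for INCL01A and OTH12 only, so OTH14 subjects remain. The sensitivity analysis in SAP 2.5.4 drops them along with subjects under 12 other codes.

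The scoring rules are in Protocol Appendix 4:

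- **Mouth, Table 16-3.** Complete response is "NIH Modified OMRS 0 after previous involvement". The unchanged column of the same row includes a "change of OMRS from baseline less than 2 points".
- **Joints, Table 16-3.** Complete response needs a joint score of 0 and "P-ROM score 25 after previous involvement by at least 1 measure".
- **Joints, Section 16.4.2.3.** "Involvement at baseline is defined as NIH Joint and Fascia score" of 1 or more; P-ROM does not enter.

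Table 16-5 makes the overall response partial when at least one organ with baseline involvement improves and none progresses.

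**The concern.** The sponsor has a code for responses that do not follow the criteria, so it expects some and has a way of identifying them. The plan then offers two treatments: keep the entered category, or delete the subject. Neither shows how the child would be classified under the criteria. Deletion also changes the denominator and mixes scoring errors with dosing, taper, compliance and eligibility deviations, so a shift in the rate could not be traced to scoring.

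The Appendix 4 conflicts are a separate matter. Two sites could apply the protocol correctly to identical scores and report different primary outcomes. Neither would have committed a deviation, so OTH14 would not reveal it. In a single-arm, open-label trial there is no comparator in which such differences could cancel.

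**Working it through.** **1. The plan's own figure.** Protocol Table 12-1 and SAP Table 3-1 give, for n = 42 and a true rate of 70%, a minimum of 27 responders, probability 0.836 and a 90% interval of 0.505 to 0.765.
- Probability: the sum over x = 27 to 42 of C(42, x) × 0.7^x × 0.3^(42−x) = 0.8360.
- Clopper-Pearson limits: lower = Beta quantile(0.05; x, n−x+1); upper = Beta quantile(0.95; x+1, n−x). For 27/42 these are 0.5045 and 0.7653.

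All 21 rows of the table reproduce. The sample-size figures are correct and this point does not affect them.

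**2. Mouth rule.** With the modified OMRS running from 0 to 12 there are 13 × 13 = 169 baseline and follow-up pairs. Let complete response take precedence over partial response when both apply. Exactly one pair then falls in two columns: 1 to 0, which is both complete response and unchanged.

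**3. Joint rule.** Take baseline joint score 0 and P-ROM 24, then score 0 and P-ROM 25. Table 16-3 calls this complete response, because one measure was involved. Under 16.4.2.3 the organ was not involved at baseline, so under Table 16-5 it cannot support an overall response.

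**4. Consequence for the child.** Assume no new systemic therapy and every other organ unchanged or not involved.

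| Change | First reading | Second reading |
|---|---|---|
| OMRS 1 to 0 | organ CR, overall PR, responder | unchanged, non-responder |
| Joint score 0 with P-ROM 24 to 25 | organ CR, overall PR, responder | not involved, overall unchanged, non-responder |

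If another involved organ improves and none progresses, the child is a responder under both readings. If another organ progresses, the child is a non-responder under both.

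**5. Size per subject.** 100/46 = 2.17 points with all 46 enrolled subjects (Protocol, Amendment 2); 100/42 = 2.38 at the planned 42. The Full Analysis Set size is not stated, and OTH12 subjects are removed from it. Exact 90% intervals at n = 46 around the planned rate (0.70 × 46 = 32.2):

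| Responders | Rate | 90% interval |
|---|---|---|
| 34 | 73.9% | 0.612 to 0.842 |
| 33 | 71.7% | 0.589 to 0.824 |
| 32 | 69.6% | 0.566 to 0.806 |
| 31 | 67.4% | 0.543 to 0.787 |
| 30 | 65.2% | 0.521 to 0.768 |
| 29 | 63.0% | 0.499 to 0.749 |

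Reclassifying one, two or three subjects moves the rate by 2.2, 4.3 or 6.5 points, in either direction. These counts are illustrative; the documents give none.

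**6. Data for a derivation.** For mouth, Protocol 8.3.1.2.1 says: "The total score for all mucosal changes will populate the overall mouth organ score in the eCRF". It says the same of skin, and Protocol 8.4.1 puts laboratory results and normal ranges on the eCRF. Eye, GI, lung, joint and P-ROM scores are described as part of the assessment. Their presence on the eCRF is an inference, supported by the SAP deviation codes for missing individual organ assessments.

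**The case against.** Clinician assessment is a deliberate choice: Protocol 4.1 cites a study in which clinician-reported response at six months predicted survival. The protocol provides validation checks (11.1), queries before lock (11.2) and full verification of primary-variable data (11.3). The mouth conflict is one pair in 169 and has a natural resolution: Table 16-3 attributes its response columns to the published NIH table, and the liver scheme in Figure 16-1 tests for complete response first. Responder status turns on these rules only when no other organ changes the result, in children with moderate or severe disease. A mechanical derivation could also do harm, because an organ abnormality with a documented non-GvHD cause is still scored (8.3.1.2.1) and the choice between FEV1 and symptom score depends on whether lung function tests are available or reliable (16.4.2.2). SAP 2.5.4 already plans organ-specific responses and a full category breakdown.

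Most of this stands as a limit on size and on the form of the remedy. It does not remove the point. Verification against source tests transcription, not whether a category follows Table 16-3. The natural reading of the mouth row is not written down, and the joint definitions still disagree.

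Three stronger readings are tempting, and the documents do not support them:
- **That documented errors certainly remain and favour response.** Queries may correct them, no OTH14 count is given, and the direction is unknown.
- **That Protocol 12.4.1 demands a two-point mouth improvement.** That figure is an example within the partial-response definition.
- **That one misreading could reverse the trial's conclusion.** SAP 2.5.2 plans no hypothesis test, and 50% is only a sample-size reference.

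**Conclusion.** The point holds in a limited form. The primary rate depends on an unblinded physician's entry. No planned analysis shows the rate that the written criteria give, and two scoring rules allow identical scores to count as response or non-response. Each affected subject is worth about 2.2 points at n = 46. The 50% planning reference would be crossed by a single subject only at the boundary count of 30 responders; from 32, near the planned rate, it would take three.

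The conclusion assumes that entered categories are not routinely re-scored outside the documents and that the organ scores are held as data. The documents show neither that the reported rate is wrong nor in which direction it might be.

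**What to change.** 1. Reconcile Table 16-3 with Section 16.4.2.3, and the two mouth columns with each other, so that each set of mouth and joint scores has one category. State the rule in the SAP derivation rules. It should be consistent with the NIH response table reproduced in Appendix 3 and identical for overall complete and overall partial response; a rule that applies to only one of them would recreate the double category. If any subject is affected, show the response rate under the other reading as well.
2. Add to SAP 2.5.4 a supplementary response rate at Cycle 7 Day 1, and at Cycle 4 Day 1. Derive it by program from the recorded organ scores, laboratory values, FEV1 or lung score and P-ROM, using Tables 16-3 and 16-5. Apply the recorded non-GvHD attribution and lung-function-test availability. Report it beside the CRF-reported rate with a concordance table.
3. Add a sensitivity analysis that keeps OTH14 subjects with their derived response instead of deleting them.

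The CRF-reported rate stays primary. SAP 2.5 does not repeat the primary and supportive analyses for the final report if the data are unchanged. The new analyses must therefore be listed for that report explicitly and labelled as added after the interim report. No new data are needed. The cost is one derivation program and a sentence explaining any difference between the derived and reported rates.
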